7.4.5 Subgroup Analysis

In order to evaluate homogeneity of treatment effects across subjects with different demographic and baseline characteristics, subgroup analysis of the efficacy variables will be performed, respectively. The subgroups in Section 7.8 will be analyzed.

7.5 Analysis of Safety

[Analysis Set: SAF]

Details for analysis of safety will be described in 10.2 Appendix 2: Overview of AE analysis, and, 10.3 Appendix 3: Overview of Clinical Laboratory Evaluation, Vital Signs, and Electrocardiograms (ECGs) analyses.

7.5.1 Adverse Events

Treatment emergent adverse events (TEAEs) in this study will be defined as below:

• Any adverse event that started or worsened in severity after the first dose of study drug at RAJ2 to the end of the final observation

Any unrecovered adverse event that first occurred during the preceding studies (RAJ1, RAJ3, and RAJ4) will be treated as medical conditions and not treated as TEAEs in this study.

A drug-related TEAE is defined as any TEAE with possible, probable or missing relationship to study drug as assessed by the investigator. Moreover, any TEAE with missing relationship to study drug or reference drug was counted as drug related (probable).

Adverse events will be coded using the MedDRA.

All adverse events reported during the study period will be presented in subject listings.

In this study 2 types of analyses for TEAEs will be performed:

- TEAE occurrence analysis
- TEAE per 100 patient-years analysis

TEAE occurrence analysis will be displayed by whole treatment period, unless specifically stated otherwise. TEAE per 100 patient-years analysis will be displayed the following category, and by overall period.

- \circ 0 6 months
- 6 <- 12 months
- o 12 <- 24 months
- 24 <- 36 months
- o 36 <- 48 months
- 48 <- 60 months
- \circ 60 <- 72 months
- o 72 <- 84 months
- o 84 months <

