### **5.2.2 Medical History**

Diseases that remain uncured at the time of the first dose of study drug will be regarded as concurrent diseases. All concurrent diseases will be investigated, and the name of the diagnosis and the time of onset will be recorded in the medical record or other source document, as well as in the CRF (for subjects who were transferred from studies RAJ3 or RAJ4, the onset date of concurrent diseases does not need to be recorded in the CRF). Moreover, AEs that have continued to be present since studies RAJ1, RAJ3, or RAJ4 will be recorded in the CRF.

Previous diseases need not be recorded in the CRF.

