## 5.5 Adverse Events and Other Safety Aspects

### 5.5.1 Definition of Adverse Events (AEs)

An AE is defined as any untoward medical occurrence in a subject administered a study drug that does not necessarily have a causal relationship to this treatment. An AE can therefore be any unfavorable and unintended sign (including an abnormal laboratory finding), symptom, or disease temporally associated with the use of a study drug, whether or not related to the study drug.

All AEs newly observed in the period from the first dose of study drug to end of study (at time of follow-up) or spontaneously reported AEs will be recorded in the medical record or other source document, as well as in the CRF. If a concurrent disease has clearly worsened to an extent that exceeds the usual course after the first dose of the study drug, it will be mentioned among the AEs as a worsening of a concurrent disease. If an AE recurs after having temporarily disappeared, it will be handled as a new AE.

An abnormality identified during a medical test (e.g., laboratory parameter, vital sign, ECG data, physical examination) should be defined as an AE only if the abnormality meets one of the following criteria:

- Induces clinical signs or symptoms
- Requires active intervention
- Requires suspension, interruption, or discontinuation of study medication
- The abnormality or laboratory test value is clinically significant based on the opinion of the investigator or other responsible personnel

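### SAP 7.5.1 gives conflicting rules for adverse events carried over from the parent studies that worsen in RAJ2

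*SAP*

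**What the plan says.** SAP 7.5.1 defines a TEAE as "Any adverse event that started or worsened in severity after the first dose of study drug at RAJ2 to the end of the final observation". It then adds a rule for carry-over. The rule applies to "Any unrecovered adverse event that first occurred during the preceding studies", and it names RAJ1, RAJ3 and RAJ4 as those studies. Its effect is that such events "will be treated as medical conditions and not treated as TEAEs in this study".

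The protocol deals with the same events in two places. Section 5.2.2 states: "Diseases that remain uncured at the time of the first dose of study drug will be regarded as concurrent diseases". It then separately provides that "AEs that have continued to be present since studies RAJ1, RAJ3, or RAJ4 will be recorded in the CRF". Section 5.5.1 covers deterioration: "If a concurrent disease has clearly worsened to an extent that exceeds the usual course after the first dose of the study drug", then "it will be mentioned among the AEs as a worsening of a concurrent disease".

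SAP 7.1, in its rules for missing AE onset dates, treats the RAJ2 AE page and the page for parent-study AEs as separate sources.

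**The concern.** The worsening limb of the TEAE definition has work to do only for events that began before the first RAJ2 dose; anything that begins later already qualifies as a new event. The carry-over rule removes parent-study events that have not resolved, which are among the events that limb is there to catch. A programmer who lets the specific rule override the general one would leave a carried-over Grade 1 event that reaches Grade 3 out of the TEAE tables.

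Long-term safety is a stated objective of the study. The tables of serious, Grade 3 or higher, discontinuation-related and special-interest events in SAP 7.5.1.1, and the patient-year rates in 7.5.1.2, all use the TEAE definition. Any error from the exclusion goes one way, towards fewer events.

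**Working it through.** No arithmetic applies. The point is about classification, and the plan gives no count of carried-over or worsened events. The check sets the rules side by side for each kind of carried-over event.

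| Carried-over event in RAJ2 | TEAE definition (SAP 7.5.1) | Carry-over rule (SAP 7.5.1) | Protocol 5.5.1 | Result |
|---|---|---|---|---|
| Severity unchanged | Not a TEAE | Not a TEAE | No new entry | No conflict; correctly excluded |
| Clearly worse than its usual course | TEAE | Not a TEAE, if the entry is seen as the same event | Entered among the RAJ2 AEs | Depends on how the SAP is read |
| More severe, but not clearly beyond its usual course | TEAE | Not a TEAE | No provision for a new entry | Excluded, against the definition |
| Resolves, then recurs | TEAE | Does not apply once recovered | Handled as a new AE | No conflict |

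**Second row.** An entry on the RAJ2 AE page would naturally carry a RAJ2 onset date. SAP 7.1 supports this: an imputed onset that falls too early is reset to the first RAJ2 dose for the RAJ2 page, and to the first parent-study dose for the parent-study page. But the carry-over rule turns on where the event first occurred, and the SAP does not say whether a worsening entry counts as a new event for that purpose.

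**Third row.** The protocol threshold (clear worsening, beyond the usual course) is higher than the SAP threshold (any increase in severity). Events between the two meet the SAP definition and are still excluded.

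**Laboratory events.** Protocol 5.2.2 speaks of uncured diseases and then mentions continuing AEs separately, so it is not certain that a continuing laboratory AE counts as a concurrent disease under 5.5.1. This matters for this drug. Over the overall period of RAJ3 and RAJ4, Protocol 1.3 reports increased CPK in 5.7% to 11.5% of the 100 mg and 150 mg groups, and abnormal hepatic function in 1.9% to 7.8%.

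**Where excluded events go.** They become medical conditions, but SAP 7.2.2.4 summarises medical conditions at the parent-study baseline, before those AEs began. The demographic table in 7.2.2.1 has a yes/no line for complications at Week 0, which identifies no event. As named adverse events they appear only in the subject listings.

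**Dating the worsening.** Protocol 5.5.1 has severity recorded at its peak, as one item per event. A carried-over record showing Grade 3 does not by itself say whether Grade 3 was reached before or after Week 0.

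**The case against.** The two sentences can be read so that both have effect: the unresolved parent-study event is background, and its worsening is a RAJ2 event. The protocol's provision for worsening of concurrent diseases and the separate CRF pages both support that reading. The gravest cases are also the least likely to be missed. Worsening to hospitalisation or a life-threatening state would ordinarily exceed the usual course. Protocol 5.5.6 requires immediate reporting when an AE under follow-up becomes serious. All AEs reported in the study period are listed. Laboratory deterioration is summarised whatever its TEAE status, through changes and shifts from Week 0, toxicity grades and liver criteria (SAP 7.5.2).

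Most of this stands, and it rules out two stronger readings. A reader might infer that worsened carry-over events are never counted; the documents do not support that, because clear worsening can enter the tables as a RAJ2 AE. A reader might also infer that the missing events are mainly high-grade ones; the only sure gap is below the protocol threshold, which points the other way.

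The objection does not remove the conflict. The reading that reconciles the two sentences is not written in the SAP, and it does not help increases in severity below the protocol threshold. Listings and immediate reporting do not put an event into an incidence table.

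**Conclusion.** The contradiction in SAP 7.5.1 is real and should be resolved. Its certain effect is limited to carried-over events that become more severe without clearly exceeding their usual course. Its possible effect extends to clear worsening entered under Protocol 5.5.1, if the carry-over rule is applied literally.

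The size of the undercount cannot be estimated. It is tempting to start from the 87% to 89% of ASP015K subjects who had a TEAE over the overall period of RAJ3 and RAJ4 (Protocol 1.3), but that figure counts any event and does not show how many were unresolved at rollover or later worsened. The overall any-TEAE percentage would also move little, since each subject is counted once and a subject with another TEAE is already included. The effect would fall on the rows by preferred term, severity and seriousness, and on the event-based patient-year rates.

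The downward direction follows from the wording alone. The conclusion assumes only that some carried-over events worsen in RAJ2 and that programming follows the SAP text.

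**What to change.** Make three changes to SAP 7.5.1 before data lock:

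1. Add to the carry-over sentence: *unless it worsens in severity or becomes serious after the first dose of study drug in RAJ2*.
2. State that worsening recorded among the RAJ2 AEs under Protocol 5.5.1 is a TEAE, with onset at the date of worsening.
3. State where that date comes from for carried-over events. Because severity is held only at its peak, identification should rest on a worsening entry on the RAJ2 AE page. For carried-over events without such an entry, say whether sites will be queried, or state that the worsening cannot be identified.

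If the database is already locked, the SAP Introduction allows a change from plan that is justified in the clinical study report.

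The cost is a few sentences, a little extra data handling and possibly some queries; no new visits or assessments are needed. TEAE rates may rise slightly.

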7.5.1.1 Adverse events

The coding dictionary for this study will be MedDRA 11.1. It will be used to summarize AEs by SOC and PT. Subjects reporting more than one AE for a given MedDRA PT will be counted only once for that term. Subjects reporting more than one AE within a SOC will be counted only once for the SOC total. Subjects reporting more than one AE will be counted only once in the overall AE total.

SOCs will be presented by descending frequency for "Total" (RAJ1 + RAJ3 + RAJ4) column, and PTs within SOC will be presented by decreasing frequency in "Total".

Number and percentage of subjects with TEAE in the following AE categories will be summarized by SOC and PT:

An overview table will include the following details:

- Number and percentage of subjects with TEAE
- Number and percentage of subjects with drug related TEAE
- Number and percentage of subjects with death
- Number and percentage of subjects with serious TEAE
- Number and percentage of subjects with drug related serious TEAE
- Number and percentage of subjects with Grade 3 or Higher in Severity TEAE
- Number and percentage of subjects with TEAE leading to permanent discontinuation of study drug
- Number and percentage of subjects with drug related TEAE leading to permanent discontinuation of study drug
- Number and percentage of subjects with serious TEAE leading to permanent discontinuation of study drug
- Number and percentage of subjects with drug related serious TEAE leading to permanent discontinuation of study drug
- Number and percentage of subjects with TEAE leading to dose decrease of study drug
- Number and percentage of subjects with drug related TEAE leading to dose decrease of study drug
- Number and percentage of subjects with TEAE leading to temporary discontinuation of study drug
- Number and percentage of subjects with drug related TEAE leading to temporary discontinuation of study drug

The number and percentage of subjects with TEAEs, as classified by SOC and PT will be summarized by preceding studies and overall. Summaries will be provided for:

- TEAEs
- Drug related TEAEs, defined as any TEAE with possible, probable or missing relationship to study drug as assessed by the investigator.
 Subjects reporting more than one TEAE for a given PT will be counted only once for that term in the most related category reported.

In addition, the number and percentage of subjects with TEAEs and Drug related TEAEs, as classified by SOC and PT will be presented by preceding studies and overall, by Maximum Dose of Study Drug.

- Serious TEAEs
- Drug related serious TEAEs
- TEAEs by severity based on National Cancer Institute Common Terminology Criteria for Adverse Events (NCI-CTCAE) Grade (Grade 1 = mild, Grade 2 = moderate, Grade 3 = severe or medically significant, Grade 4 = life threatening, Grade 5 = death related to AE)

Subjects reporting more than one TEAE for a given PT will be counted only once for that term in the most severe category reported.

If a subject has an AE which has a missing severity, then the subject will be counted in the severity category of "Missing" (i.e., missing severity will not be imputed).

- Drug related TEAEs by severity
- Grade 3 or higher TEAEs by severity
- TEAEs by relationship to study drug

Subjects reporting more than one TEAE for a given PT will be counted only once for that term in the most related category reported.

TEAE with missing relationship to study drug missing will be counted as drug related. Moreover, any TEAE with missing relationship to study drug or reference drug was counted as drug related (probable).

- TEAEs leading to death
- TEAEs leading to permanent discontinuation of study drug
- Drug related TEAEs leading to permanent discontinuation of study drug
- Serious TEAEs leading to permanent discontinuation of study drug
- Drug related serious TEAEs leading to permanent discontinuation of study drug
- TEAE leading to dose decrease of study drug
- Drug related TEAE leading to dose decrease of study drug
- TEAE leading to temporary discontinuation of study drug
- Drug related TEAE leading to temporary discontinuation of study drug
- Most common TEAEs (> 5% in any preceding study)
- Most common serious TEAEs (> 5% in any preceding study)
- TEAEs excluding serious adverse events that equal to or exceed a threshold of 5% in any preceding study
- The number and percentage of subjects with TEAEs of special interest.

Following adverse events of special interest are defined:

- Serious Infections
- Malignancies
- Herpes Zoster Related Disease (Herpes Zoster and Varicella)
- Herpes Zoster
- o Varicella

Infections That Require Intravenous Anti-infectious Therapy

Note: Definition will be provided in 10.8 Appendix 8: AE of Special Interest.

In addition, the subgroup analysis of Sex, Age Group, Concomitant Steroid at Baseline, Prednisone Dose at Baseline, Body Weight (kg) at Week 0, Concomitant DMARD category at Week 0, Maximum Dose of Study Drug and Study Region will be conducted.

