#### 1.2.4 Efficacy

In a double-blind, placebo-controlled study conducted in Japan (015K-CL-RAJ1), the dose response for the efficacy and safety of once-daily oral ASP015K (25, 50, 100, 150 mg) administered for 12 weeks was investigated in 281 patients with moderate to severe RA. Its primary efficacy variable was the ACR20 response rate at Week 12. The ACR20 response rates were 10.7% for placebo, 23.6% for 25 mg, 31.6% for 50 mg, 54.5% for 100 mg, and 65.5% for 150 mg groups. Significant improvements over placebo were noted for 50 mg ( $P=0.021$ ), 100 mg ( $P<0.001$ ), and 150 mg groups ( $P<0.001$ ). In addition, logistic regression analysis demonstrated a statistically significant dose–response relationship ( $P<0.001$ ). Secondary efficacy variables, the ACR50 response rate, ACR70 response rate, and DAS28-CRP, exhibited significant improvements for ASP015K over placebo. A long-term extension study (015K-CL-RAJ2) for patients who completed this study is underway to investigate the efficacy and safety of ASP015K administered over an extended period of time.

Overseas, 3 clinical studies of patients with moderate to severe RA have been completed (015K-CL-RA21, 015K-CL-RA22, 015K-CL-RA25). 015K-CL-RA21 and 015K-CL-RA22 were dose-finding studies of ASP015K administered with and without MTX, respectively. 015K-CL-RA25 was a long-term follow-up extension study that enrolled the patients who completed either of the 2 studies.

In a US double-blind, placebo-controlled study in patients with moderate to severe psoriasis vulgaris (015K-CL-PS01), 124 subjects were orally administered ASP015K (10, 25, 60, 100 mg BID or 50 mg QD) over 6 weeks. Compared with placebo, all ASP015K groups showed greater improvements in terms of change from baseline in the PASI score (primary efficacy variable), depicting a statistically significant difference in the overall therapeutic response. For secondary efficacy variables, the treatment success based on Physician’s Static Global Assessment (PSGA) and 75% reduction in the PASI score (PASI 75 response) demonstrated the efficacy of ASP015K.

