## **5 TREATMENTS AND EVALUATION**

### **5.1 Dosing and Administration of Study Drugs and Other Medications**

#### **5.1.1 Dose/Dose Regimen and Administration Period**

(1) Starting dose (100 mg/day as ASP015K)

The subjects will take 1 tablet of ASP015K 100 mg orally QD after breakfast. The first dose will be administered at each study center at the Week 0 visit after all the scheduled assessments and tests have been completed.

\* The starting dose for subjects who transferred from study RAJ1 is 50 mg/day. After implementation of the study protocol (ver. 2.0/ver. 3.0), only subjects who transferred from studies RAJ3 or RAJ4 will be enrolled newly.

(2) Increased dose (150 mg/day as ASP015K)

The subjects will take 1 tablet of ASP015K 150 mg orally QD after breakfast.

For the subjects who have completed study RAJ1 and are continuing treatment with ASP015K at a dose of 50 mg/day, the need for a change in the dose shall be assessed at the initiation of the clinical study under the protocol ver. 2.0/ver. 3.0. If the dose is not increased to 100 mg and treatment is to be continued at a dose of 50 mg/day, the reason for this decision must be entered in the medical record.

For subjects who have been receiving ASP015K at a dose of 50 mg/day in Japan, the dose will be increased to 100 mg/day after approval in Japan. Any subjects for whom the dose cannot be increased should be withdrawn from the study. This study will be conducted as a post-marketing clinical study up to a maximum of 6 months after the NDA approval in Japan. (After the NDA approval in Japan, the post-marketing clinical study will be ended once the study drug is available in the clinical sites as a commercially available product. The planned study period will be up to a maximum of 6 months after the NDA approval in Japan). In Korea and Taiwan, this study will continue as a clinical study after the NDA approval in Japan. The duration of treatment will differ depending on the subject. Moreover, in order to prevent treatment from continuing purposelessly without effect, the investigator or the sub-investigator will investigate efficacy and safety at each study visit, confirm the appropriateness of continuing treatment for each individual subjects, and decide whether or not to continue treatment.

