7.5.1.2 Adverse Events Per 100 Patient-Years

In order to adjust for differences in subjects' durations in the study and the potential differential dropout rates between the preceding studies, TEAEs per 100 patient-years (PYs) will be calculated as follows:

Definition 1:

TEAEs per $100 \text{ PYs} = 100 \times \text{(Number of subjects who had at least 1 incidence / Total PYs)}$ Total PYs will be calculated by summing individual subjects' durations.

If subjects had at least 1 predefined AE, then the duration of these subjects are summed as from initial dose up to first incidence of predefined AEs.

If subjects had no predefined AE, then the duration of these subjects are summed as from initial dose through follow-up. Summed duration will be divided by 365.25 to represent per year.

Definition 2:

TEAEs per 100 PYs = $100 \times (Number of TEAEs for all subjects/ Total PYs)$

For number of TEAEs for all subjects, multiple occurrences of the same TEAE in the same subject will be counted multiple times.

Total PYs will be calculated by summing subjects' durations in this study through the follow-up period. Each subject's duration will be calculated as: (last date of follow-up in the study – date of initial dose of study drug + 1) / 365.25.

The number of TEAEs and TEAEs per 100 PYs will be provided by Definition 2, for all TEAEs (if analyzable) by SOC and PT for each preceding study, and Total.

Patient-Year analysis for following specified AE will also be conducted by Definition 1 with 95% confidence interval.

- Serious Infections
- Malignancies
- Herpes Zoster Related Disease (Herpes Zoster and Varicella)
- Herpes Zoster
- o Varicella
- Infections That Require Intravenous Anti-infectious Therapy

Note: Definition will be provided in 10.8 Appendix 8: AE of Special Interest.

Confidence Interval for TEAEs per 100 patient-years will be calculated for AE of special Interest based on following formula (assuming Poisson distribution).

- Upper limit of CI (TEAEs per 100 PYs): $100 \times \exp(\log(A/T) + Z_{(alpha)} * \sqrt{1/A})$
- Lower limit of CI (TEAEs per 100 PYs) : $100 \times \exp(\log(A/T) Z_{(alpha)} * \sqrt{1/A})$

A: Number of subjects who had at least 1 incidence

T: Total PYs

Z_(alpha): alpha % point of standard normal distribution

alpha = 0.025

TEAE of special interest per 100 patient-years analysis will be displayed the following category.

- \circ 0 6 months
- \circ 6 <- 12 months
- o 12 <- 24 months
- o 24 <- 36 months

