- o 36 <- 48 months
- o 48 <- 60 months
- 60 <- 72 months
- o 72 <- 84 months
- o 84 months <

In addition, the subgroup analysis of Sex, Age Group, Concomitant Steroid at Baseline, Prednisone Dose at Baseline, Body Weight (kg) at Week 0, Concomitant DMARD category at Week 0, Maximum Dose of Study Drug and Study Region will be conducted.

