7.8 Subgroups of Interest

7.8.1 Subgroup analysis of the selected efficacy endpoint (ACR20-CRP) and treatment emergent adverse events

The selected efficacy variable (ACR20-CRP) and TEAEs will be summarized for the subgroups defined on the basis of the categorized variables listed below:

- Sex (Male, Female,)
- \circ Age Group at Week 0 (< 65 years, >= 65 years)
- Prior Anti-TNF DMARD Use in preceding study (User, Non-user)
- Prior Biologic DMARD-IR in preceding study (No. Yes)

- Duration of RA (years) in preceding study (< 5 years, >= 5 years)
- Number of Prior DMARDs Used in preceding study $(0, 1, 2, \ge 3)$
- \circ Number of Prior Biologic DMARDs Used in preceding study $(0, 1, 2, \ge 3)$
- MTX Dose (mg/week) at Week 0 (None, 0 <- 8 mg/week, 8 <- 12 mg/week, > 12 mg/week)
- Concomitant Steroid at Week 0 (No, Yes)
- \circ Prednisone Dose (mg/day) at Week 0 (None, 0 <- 5 mg/day, > 5 mg/day)
- Concomitant non-Biologic DMARD Use at Week 0 (No, Yes)
- Study Region (Japan, Korea, Taiwan)
- Baseline DAS28-CRP in preceding study (<= 3.2, 3.2<-5.1, > 5.1), efficacy analyses only
- Baseline DAS28-ESR in preceding study (<= 3.2, 3.2<-5.1, > 5.1), efficacy analyses only
- Baseline CRP in preceding study (< 1.0, >= 1.0), efficacy analyses only
- Concomitant DMARD category at Week 0 (MTX, DMARD except for MTX only, None)
- Body Weight (kg) at Week 0 (<- 40 kg, 40 kg <- 60 kg, 60 kg <- 80 kg, > 80 kg)
- Maximum Dose of Study Drug (50 mg, 100 mg, 150 mg)

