10.2 Appendix 2: Overview of AE analysis

Tables below summarize AE occurrence analysis, SOC/PT analysis, and Patient-year analysis with "X" indicating that the variable will be analyzed. All analyses will be based on the SAF and presented by preceding studies and overall, unless otherwise specified.

The overview of AE occurrence analysis

	Study for Analysis			Analysis Crayn	
	RAJ1	RAJ3	RAJ4	Analysis Group	
Number and percentage of subjects with TEAE		•	•		
Number and percentage of subjects with drug related TEAE					
Number and percentage of subjects with death					
Number and percentage of subjects with serious TEAE					
Number and percentage of subjects with drug related serious TEAE					
Number and percentage of subjects with Grade 3 or Higher in Severity TEAE					
Number and percentage of subjects with TEAE leading to permanent discontinuation of study drug		X		preceding studies and overall	
Number and percentage of subjects with drug related TEAE leading to permanent discontinuation of study drug					
Number and percentage of subjects with serious TEAE leading to permanent discontinuation of study drug					
Number and percentage of subjects with drug related serious TEAE leading to permanent discontinuation of study drug					

The overview of the number of SOC/PT analysis

	Study for Analysis			A salada Gara
	RAJ1	RAJ3	RAJ4	Analysis Group
TEAEs	X	X	X	preceding studies and overall
TEAEs by maximum dose of study drug	X	X	X	preceding studies and overall
Drug related TEAEs by maximum dose of study drug	X	X	X	preceding studies and overall
Drug related TEAEs	X	X	X	preceding studies and overall
Serious TEAEs	X	X	X	preceding studies and overall

	Study for Analysis			
	RAJ1	RAJ3	RAJ4	- Analysis Group
Drug related serious TEAEs	X	X	X	preceding studies and overall
TEAEs by severity	X	X	X	preceding studies and overall
Drug related TEAEs by severity	X	X	X	preceding studies and overall
TEAEs leading to permanent discontinuation of study drug	X	X	X	preceding studies and overall
Drug related TEAEs leading to permanent discontinuation of study drug	X	X	X	preceding studies and overall
Serious TEAEs leading to permanent discontinuation of study drug	Х	X	X	preceding studies and overall
Drug related serious TEAEs leading to permanent discontinuation of study drug	Х	X	X	preceding studies and overall
Grade 3 or higher TEAEs by severity	X	X	X	preceding studies and overall
TEAEs by relationship to study drug	X	X	X	preceding studies and overall

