TEAEs leading to death	X	X	X	preceding studies and overall
Most common TEAEs (> 5% in any preceding study)	X	X	X	preceding studies and overall
Most common serious TEAEs (> 5% in any preceding study)	X	X	X	preceding studies and overall
TEAEs excluding serious adverse events that equal to or exceed a threshold of 5% in any preceding study	X	X	X	preceding studies and overall
TEAEs of special interest Serious Infections Malignancies Herpes Zoster Related Disease (Herpes Zoster and Varicella) Herpes Zoster Varicella Infections That Require Intravenous Anti-infectious Therapy	X	х	х	preceding studies and overall
TEAEs by subgroups Sex (Male, Female,) Age Group at Week 0 (< 65 years, >= 65 years) Prior Anti-TNF DMARD Use in preceding study (User, Non-user) Prior Biologic DMARD-IR in preceding study (No, Yes) Duration of RA (years) in preceding study (< 5 years, >= 5 years) Number of Prior DMARDs Used in preceding study (0, 1, 2, >= 3) Number of Prior Biologic DMARDs Used in preceding study (0, 1, 2, >= 3) MTX Dose (mg/week) at Week 0 (None, 0 <- 8 mg/week, 8 <- 12	Х	X	X	preceding studies and overall

	Study for Analysis			Analysis Green
	RAJ1	RAJ3	RAJ4	Analysis Group
mg/week, > 12 mg/week)				
Concomitant Steroid at Week 0 (No, Yes)				
• Prednisone Dose (mg/day) at Week 0 (None, 0 <- 5 mg/day, > 5 mg/day)				
• Concomitant non-Biologic DMARD Use at Week 0 (No, Yes)				
Study Region (Japan, Korea, Taiwan)				
• Concomitant DMARD category at Week 0 (MTX, DMARD except				
for MTX only, None)				
TEAEs of special interest by subgroups				
• Sex (Male, Female,)				nraading
• Age Group at Week 0 (< 65 years, >= 65 years)	X	X	X	preceding studies and
• Concomitant Steroid at Week 0 (No, Yes)	Λ	Λ	Λ	overall
• Prednisone Dose (mg/day) at Week 0 (None, 0 <- 5 mg/day, > 5				Overan
mg/day)				

Patient-year analysis

	Study for Analysis			
	RAJ1	RAJ3	RAJ4	Analysis Group
TEAEs ^{1, 3}	X	X	X	preceding studies and overall
 TEAEs of special interest² Serious Infections Malignancies Herpes Zoster Related Disease (Herpes Zoster and Varicella) Herpes Zoster Varicella Infections That Require Intravenous Anti-infectious Therapy 	X	X	X	preceding studies and overall
 TEAEs of special interest by subgroups ² Sex (Male, Female,) Age Group at Week 0 (< 65 years, >= 65 years) Concomitant Steroid at Week 0 (No, Yes) Prednisone Dose (mg/day) at Week 0 (None, 0 <- 5 mg/day, > 5 mg/day) 	Х	X	X	preceding studies and overall

¹ According to Definition 2
² According to Definition 1

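### Adverse events by RAJ2 dose are grouped only by each subject's maximum dose, so lower-dose events are reported under a higher dose; add rates by dose at onset

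*SAP*

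**What the plan says.** **Dose grouping.** SAP 7.5.1.1 says that the tables of TEAEs and drug-related TEAEs "as classified by SOC and PT will be presented by preceding studies and overall, by Maximum Dose of Study Drug". Appendix 2 has the matching rows, for example "Drug related TEAEs by maximum dose of study drug". Maximum dose is also a subgroup factor in SAP 7.8.1 and, for events of special interest, at the end of 7.5.1.1 and of 7.5.1.2. The 7.5.1.2 sentence, in the patient-year section, ends "Maximum Dose of Study Drug and Study Region will be conducted". All other adverse-event tables are by preceding study, overall, time since first dose or a baseline subgroup. The Treatment Sequence Set in SAP 7.1 describes treatment in the preceding study, not in RAJ2.

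**Person-time.** Under Definition 1 in SAP 7.5.1.2, time runs from the first RAJ2 dose to the first event. Otherwise: "If subjects had no predefined AE, then the duration of these subjects are summed as from initial dose through follow-up". Definition 2 uses the whole time in study, and its rates are reported by preceding study and in total. Neither is cut at a dose change.

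**Dosing.** For RAJ3 and RAJ4 entrants, Protocol 5.1.1 says "The subjects will take 1 tablet of ASP015K 100 mg orally QD after breakfast" as the starting dose; RAJ1 entrants start at 50 mg. Under Protocol 5.1.2, moving to 150 mg needs at least 4 weeks on 100 mg, a DAS28-ESR of 3.2 or more on a visit day, and an acceptable safety judgement at that visit. Reductions to 50 mg also occur: SAP 7.2.1 plans a disposition table for those subjects.

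**Efficacy, by contrast.** SAP 7.4.3 drops data after the initial dose changes, and 7.4.4 aligns data to the first dose increase. Safety has no counterpart.

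**The concern.** A column headed 150 mg suggests what happened on 150 mg. Here it shows what happened at any time to subjects who at some point took 150 mg. Events before escalation, or on 50 mg after a reduction, are included. Membership is settled after baseline, because a subject must stay in the study long enough to be escalated.

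The SOC/PT tables are percentages with no time denominator, so columns with different follow-up are not comparable. SAP 7.5.1.2 itself introduces patient-year rates because durations differ.

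Readers will look at these columns with a dose question in mind. Long-term safety is a study objective (Protocol 2.1). Protocol 1.3 reports CPK increases in RAJ1 of 1.8% on 100 mg and 12.1% on 150 mg, and drug-related TEAEs in RAJ4 to Week 12 of 32.8% and 46.0%. The plan gives no other adverse-event summary by RAJ2 dose against which to check the impression.

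**Working it through.** The documents state no figure for this point, so there is none to reproduce.

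**1. Lower-dose time in the 150 mg column, from the protocol's rules alone.** Six months = 6 × 30.4375 = 182.6 days (SAP 6.5 uses 30.4375 days per month). The minimum on 100 mg is 28 days (Protocol 5.1.2). Weeks 2, 4 and 8 are for RAJ1 subjects only (Protocol Table 1, note v), so the first scheduled RAJ3/RAJ4 visit after Week 0 is Week 12, after 84 days. For a subject followed through the period:

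- escalation at 28 days: 28/182.6 = 15.3% of the first 6 months on 100 mg
- at Week 12: 84/182.6 = 46.0%
- at Week 24: 168/182.6 = 92.0%

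Over an assumed 3 years (1,095.75 days) the shares are 2.6%, 7.7% and 15.3%. The problem is largest in the early time bands and for late escalators.

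**2. Effect on a Definition 1 rate (assumed inputs).** Let the first-event rate be 3 per 100 PY on 100 mg and 6 on 150 mg, with follow-up T = 3 years, escalation at time t, and no link between event and escalation. For the 150 mg column:

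- P(event) = 1 − exp[−0.03t − 0.06(T − t)]
- PY per subject = [1 − exp(−0.03t)]/0.03 + exp(−0.03t) × [1 − exp(−0.06(T − t))]/0.06

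| t (years) | P(event) | PY | Rate per 100 PY | Ratio to 3.0 |
|---|---|---|---|---|
| 0.23 (Week 12) | 0.159 | 2.764 | 5.75 | 1.92 |
| 1 | 0.139 | 2.814 | 4.95 | 1.65 |
| 2 | 0.113 | 2.855 | 3.96 | 1.32 |

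A true doubling reads as 1.3 to 1.9. With no dose effect, both columns read 3.0.

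**3. Effect on percentages (assumed inputs).** Take 3 per 100 PY on both doses, with mean follow-up of 2 years in the 100 mg column and 3 years in the 150 mg column. Then 1 − exp(−0.06) = 5.8% against 1 − exp(−0.09) = 8.6%, an apparent ratio of 1.48 with no dose effect.

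**4. Wider simulated range (assumed inputs).** The grid used rates of 3 to 7 per 100 PY and discontinuation of 0.12 to 0.25 per year. Between 0 and 8% of events stopped treatment. Escalation was at 0.2 to 0.4 per year after 4 weeks, or in 40 to 60% of subjects by Week 12 or 24. Follow-up was about 3 years. The 150:100 ratio of Definition 1 rates was 0.91–1.04 with no effect and 1.40–1.92 under a doubling. The ratio of percentages with no effect was 1.03–1.58, reaching about 1.85 if follow-up ranges over 2 to 4 years.

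**5. Are the rates by maximum dose planned?** SAP 7.5.1.2 says yes for events of special interest. Appendix 2 has two lists headed "TEAEs of special interest by subgroups", one for occurrence and one for patient-years. Both contain only sex, age, steroid use and prednisone dose. If Appendix 2 governs, no exposure-adjusted rate by RAJ2 dose exists.

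**6. Who is in the 50 mg column?** Only RAJ1 subjects can be, since all others start at 100 mg. RAJ1 was run in Japan (Protocol 1.2.4). Protocol 5.1.2 has Japanese subjects on 50 mg raised to 100 mg or withdrawn after approval, which would leave mostly early leavers in the column. SAP 3.2 instead ends the study at approval, and the Kaplan-Meier table in SAP 7.3.1 censors time on initial 50 mg at study completion. The documents conflict.

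**The case against.** The study is open-label and not randomised, and has no dose-comparison objective. Protocol 7.5 tallies safety by preceding study, so the maximum-dose tables are supplementary. Escalation follows active disease, so rates by dose at onset stay confounded. In RAJ4, herpes zoster was lower on 150 mg (6.9% on 100 mg, 3.4% on 150 mg), and Protocol 1.3 reports no dose dependency for serious infections and zoster. The Appendix 2 mismatch is not specific to dose: body weight, DMARD category and region are missing from the same lists. All of this stands. It limits the weight of the point but does not remove the misallocation.

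Three stronger readings are tempting, and the documents do not support them.

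- *The tables could reverse a dose effect.* That needs an event on 100 mg generally to prevent escalation. Protocol 5.1.2 asks only for an acceptable safety judgement on the visit day, so a resolved event does not bar a later increase. Malignancy is a discontinuation criterion (Protocol 3.4), so outcome-driven membership is real there, but few events are likely. At the tofacitinib rate of 0.55 per 100 PY in Protocol 1.4 and an assumed 1,660 to 1,990 PY, 0.0055 × PY gives 9 to 11, and chance would dominate.
- *Everyone in the 50 mg column left early.* This follows from Protocol 5.1.2 but not from SAP 3.2 and 7.3.1.
- *All adverse-event rates by dose are distorted.* Rates by maximum dose appear only in 7.5.1.2, for events of special interest, and not in Appendix 2. The main SOC/PT tables by maximum dose are percentages.

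**Conclusion.** The point holds as a matter of text: maximum dose is the only RAJ2-dose grouping of adverse events, person-time is never split by dose, and lower-dose events therefore appear under a higher dose. The 28-day minimum (15% of the first 6 months) and the Week 12 figure (46%) come from the documents. Every effect on a ratio rests on assumed escalation, event and follow-up values. On those, rates for common events are diluted modestly and are close to unbiased when there is no dose effect, while percentages can show a pattern that comes from unequal follow-up. It is an improvement to consider in descriptive tables, not a flaw in a primary result.

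**What to change.** - For TEAEs and events of special interest, add number of events, person-years and rate per 100 PY by dose at onset (50, 100, 150 mg). Split person-time at each recorded dose change, and state a rule for time off drug and for the follow-up period.
- Keep the maximum-dose tables, show follow-up per column, and label them descriptive and not a dose comparison.
- Reconcile the subgroup sentences in SAP 7.5.1.1 and 7.5.1.2 with the lists in Appendix 2.
- Reconcile Protocol 5.1.2 with SAP 3.2 and 7.3.1 on subjects still on 50 mg at Japanese approval.
- State the limits: escalation is not randomised, and dose at onset suits long-latency events such as malignancy poorly. An ever/never 150 mg view, with ever counted from the first 150 mg dose, is optional.

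The data exist: dose changes are recorded in the CRF (Protocol 5.1.2), onset dates are collected (Protocol 5.5.1), and the SAP already uses duration by dose level (6.5) and time to dose change (7.3.1). The cost is SAP wording, some extra programming for the split and the off-drug rule, and some sparse cells. Nothing in trial conduct changes.
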